II. SPECIFIC AIMS

Aim 1: To assess rTMS induced changes in functional connectivity in cortico-limbic networks

Hypothesis 1.1: At baseline, MDD patients will have abnormally increased cortico-limbic connectivity.⁸⁻¹¹

Hypothesis 1.2: rTMS to DLPFC will differentially modulate this connectivity, depending on whether positively or negatively correlated regions are targeted; and one of these targets will more robustly alter this connectivity.

Hypothesis 1.3: Connectivity changes will be more pronounced in MDD patients than in controls.

Aim 2: To assess cortico-limbic network dynamics in MDD by comparing rTMS induced changes in local glucose metabolism to rTMS induced changes in distributed connectivity

Hypothesis 2.1: 20Hz will comparably increase FDG uptake at both DLPFC stimulation sites in both groups.

Hypothesis 2.2: Stimulation of the two sites will differentially impact FDG uptake at sgACC, and will have a differential impact upon the strength of connectivity between sgACC and the stimulation site.

Hypothesis 2.3: The direction and magnitude of FDG changes at sgACC will predict the direction and magnitude of the associated changes in cortico-limbic connectivity.

Hypothesis 2.4: Local and distributed changes will be altered in MDD, reflecting aberrant network dynamics.

Hypothesis 2.5: Stimulation of a control site in parietal cortex or the cerebellum will not appreciably alter cortico-limbic connectivity or metabolism.

This work will better elucidate how intrinsic networks and their dynamics are altered in MDD. It will also assess how rTMS, or other neuromodulatory strategies, create the formation of more adaptive configurations. In turn, this will pollinate future trials that optimize MDD treatments through selective targeting of intrinsic networks.

III. SUBJECT SELECTION

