Specifically, subjects will undergo simultaneous resting-state (fcMRI)/FDG-PET imaging *without* rTMS at this first visit. The baseline PET session will serve as a comparison for changes in rCMRglu following rTMS. Critically, strong evidence supports the test re-test reliability across FDG-PET scanning sessions separated in time, provided that scanning parameters remain identical.⁷¹⁻⁷⁴ Therefore, observed metabolic changes after rTMS will be attributable to the stimulation, and will be deemed unlikely to occur as a result of inherent variability across scanning sessions. Baseline fcMRI data will serve the purpose of creating functional connectivity maps from a sgACC seed. Similar to how lpIPL was designated in Eldaief et al.¹⁴, these maps will be used to establish two cortical targets for rTMS in DLPFC: one which is positively correlated to sgACC, and another which is anticorrelated to sgACC^{21,22} (**Fig 1**). After their baseline visit, subjects will return for the first of two rTMS sessions in which they will receive 20Hz stimulation to either the positively or negatively correlated left DLPFC region. They will then return for a third session in which the alternate region is stimulated (thus enabling a within-subject design). Subjects will be randomized to a given session order, and this order will be counterbalanced across subjects. It is expected that all three visits will be completed within two months from the time of enrollment. The experimental timeline for the rTMS sessions is depicted in **Fig 5**. Immediately before stimulation subjects will be rapidly scanned with resting-state fMRI *without* PET (for approx. 25 minutes). After this, they will fill out a brief (1 min) visual analog scale in which they rate sadness, anxiety, energy, concentration, happiness, anger and disgust on a scale of 0-10. They will then be taken into a room immediately adjacent to the scanner for rTMS (i.e. constituting “off-line” stimulation⁷⁵). Subjects will be injected with FDG concurrent to the onset of rTMS. After rTMS they will again complete the mood analog scale. They will then be promptly returned to the scanner room for PET/fcMRI (within ~5 min) so as to acquire BOLD data as soon as possible after rTMS.¹⁴ Dynamic PET acquisitions will correspondingly begin at this time (e.g. at approx. 30-35 min post FDG injection), and emission data will be collected for the next 45 min.

	Visit 1	Visit 2	Visit 3	Visit 4
Obtainment of Consent	X			

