SCID questionnaire	X			
Hamilton Depression Rating Scale (HDRS)	X			
TMS screening form	X			
MRI screening form	X	X	X	X
STAT quantitative serum hcG	X	X**	X**	X**
TMS side effects questionnaire		X	X	X
Baseline fcMRI/FDG-PET without rTMS	X			
fMRI before and after rTMS; FDG-PET after rTMS		X	X	X

**Exact frequency of pregnancy testing will vary according to how far visits are apart

Table 1: Summary of study procedures by visit

VI. BIOSTATISTICAL ANALYSIS

fcMRI data: The main outcome measures of interest for fcMRI data will be the relative change in z-transformed correlation coefficients between two given cortico-limbic network regions of interest (ROIs), the difference between changes in these z-scores across conditions (e.g. correlated vs. anticorrelated stimulation), and this difference across subjects (e.g. MDD vs. controls). Six cortico-limbic regions of interest will be examined: DLPFC (the 2 stimulation sites), sgACC, dmPFC, NA and amygdala. Seed placement for sgACC will be based on MNI coordinates from other fcMRI studies.^{21,22} Anatomical location of other seeds will be determined on an individualized basis as the points of maximal positive correlation with sgACC (or negative correlation in the case of one of the DLPFC sites). Seeds will be spherical and 8mm³ in diameter. The primary correlation pair of

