interest will be DLPFC-sgACC. Based on prior studies,^{1-9,30} secondary correlation pairs of interest will be sgACC-dmPFC, sgACC-NA and sgACC-amygdala. fMRI data will be analyzed using a combination of software packages (e.g., FMRIB Software Library, FSL, Freesurfer, SPM) and custom software developed in the [name] (mentor) lab. These methods have been described in several other paradigms^{27-29,76,77} and were employed in Eldaief et al.¹⁴ We will apply a stringent in-house data quality control program to each dataset, described Yeo et al.,⁷⁸ to evaluate fMRI runs for low signal-to-noise and/or excessive head movement. Preprocessing will include global mean regression and temporal band-passing of data for signals >0.08 Hz. After preprocessing, region-to-region correlation strengths will be calculated with volumetric seed-based functional connectivity analyses: correlation maps will be produced by extracting the BOLD time course from a “seed” ROI in the brain, and then computing the Pearson's correlation coefficient (r) between that time course and the time course from all other brain voxels. Functional connectivity between two ROIs will be measured by r values, which will be transformed to the z distribution. Paired t-tests will directly compare changes in z scores before and after rTMS in a given individual, and two-sample paired t-tests will compare changes across conditions and across subjects.

FDG-PET data: MR-based motion estimates and a dual-echo ultrashort echo time MRI sequence (DUTE)⁷⁹ will be used for motion- and attenuation-correction of PET data, respectively. Other preprocessing steps will include image realignment, normalization to MNI space and smoothing. Weighted linear contrasts will then be used to identify changes in rCMRglu in the cortico-limbic regions of interest described above. Relative differences in normalized rCMRglu in these ROIs between the baseline PET scan and the post-rTMS PET scan within a given individual will be calculated on a voxel-by-voxel basis using a paired t-test. Two sample paired t-tests will compare rCMRglu changes across rTMS conditions, and across MDD patients and normals. The experimental PET and fMRI data revealing local and distributed impacts of TMS will also allow for computational analyses which will be developed with the supervision and guidance of [name] (advisor).

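### The protocol does not fix which sgACC-DLPFC pair enters the across-target test; on the stimulated-site reading that Hypothesis 2.2 suggests, target is confounded with ROI pair

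*Protocol*

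**What the plan says.** Protocol Section VI (fcMRI data) defines the main outcome as the "relative change in z-transformed correlation coefficients between two given cortico-limbic network regions of interest (ROIs"), followed by "the difference between changes in these z-scores across conditions (e.g. correlated vs. anticorrelated stimulation"). The regions are listed as "Six cortico-limbic regions of interest will be examined: DLPFC (the 2 stimulation sites), sgACC, dmPFC, NA and amygdala", so the two DLPFC sites are separate ROIs. Yet a single primary pair is named: the pair of "interest will be DLPFC-sgACC". Seeds other than sgACC are the "points of maximal positive correlation with sgACC (or negative correlation in the case of one of the DLPFC sites"). For testing, "two-sample paired t-tests will compare changes across conditions and across subjects".

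Hypothesis 2.2 in Section II says that stimulating the two sites "will have a differential impact upon the strength of connectivity between sgACC and the stimulation site". In Section I, the Fig 3 caption describes the correlated site's link with sgACC in panel B and the anticorrelated site's link in panel C.

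Each subject receives both targets, and Section V.C states: "Subjects will be randomized to a given session order, and this order will be counterbalanced across subjects". The Experimental Controls paragraph of Section VI compares pre-rTMS scans between the two sessions and checks M1, A1 and V1 for change after rTMS.

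**The concern.** Across the two rTMS sessions there are two sgACC-DLPFC pairs: one with the correlated site (P) and one with the anticorrelated site (N). The across-target test could compare one fixed pair between sessions, or the stimulated site's pair in one session with the stimulated site's pair in the other. Section VI does not choose. An analyst who follows Hypothesis 2.2 would take the second course.

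On that course the pair always travels with the target, whatever the session order, so the contrast has no way to separate a target effect from a difference in how the two pairs drift within a session. The design offers plausible sources of drift. The pre-rTMS scan is run without PET and the post-rTMS scan with it, and the post-rTMS scan follows about 25 minutes of scanning and 22.5 minutes of stimulation. More motion, drowsiness or noise in the second scan would pull a positive correlation down and a negative one up. A differential target effect under Hypothesis 2.2 could then be declared when rTMS had done nothing.

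**Working it through.** **Inputs from the protocol.** SD of the pre-to-post change 0.11 (Section III.D, from a different pair, lPIPL-mPFC); 25 subjects per group; P and N selected with opposite signs (Section VI). The plan gives no power figure for the across-target contrast, so there is none to reproduce.

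**Assumed, because the documents give no values.** Mean z of the two pairs, proportional attenuation between the scans, and the correlation between a subject's two change scores.

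**Algebra.** Let D(pair, session) be the mean pre-to-post change in signed z, with session p when the correlated site is stimulated and n when the anticorrelated site is. Write D(P,p) = cP + e(P,p), and similarly for the others. Here c is the non-specific change of that pair, the same on average in both sessions, and e is the rTMS effect.

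- Stimulated-site contrast: D(P,p) − D(N,n) = [e(P,p) − e(N,n)] + (cP − cN).
- Same-pair contrasts: D(P,p) − D(P,n) = e(P,p) − e(P,n), and D(N,n) − D(N,p) = e(N,n) − e(N,p). Both c terms are gone.
- Target term with both pairs from both sessions: ½{[D(P,p) + D(N,p)] − [D(P,n) + D(N,n)]}. Each c enters once with each sign and cancels.

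If both pairs shift by the same amount, cP = cN and the stimulated-site contrast is unbiased. If both shrink by a fraction f, cP − cN = −f(zP − zN), which is not zero because zP and zN have opposite signs.

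**One case by hand.** Take zP = +0.3, zN = −0.2 and f = 10%. The bias is −0.10 × 0.5 = −0.050. With n=25 and uncorrelated changes, SE = 0.11 × √2 / √25 = 0.031, so the bias is about 1.6 SE.

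**Simulation with no rTMS effect** (two-sided 5%, n=25, 8,000 replicates; ρ is the correlation between the two change scores):

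| Assumed mean z (P / N) | Attenuation | cP − cN | Rejection, ρ = 0 | Rejection, ρ = 0.5 |
|---|---|---|---|---|
| +0.2 / −0.2 | 5% | −0.020 | 9.1% | 13.7% |
| +0.2 / −0.2 | 10% | −0.040 | 23.8% | 42.2% |
| +0.2 / −0.2 | 20% | −0.080 | 69.1% | 93.8% |
| +0.3 / −0.2 | 5% | −0.025 | 12.1% | 19.6% |
| +0.3 / −0.2 | 10% | −0.050 | 34.9% | 58.8% |
| +0.3 / −0.2 | 20% | −0.100 | 86.5% | 99.1% |
| +0.4 / −0.3 | 5% | −0.035 | 19.4% | 32.7% |
| +0.4 / −0.3 | 10% | −0.070 | 58.1% | 85.8% |
| +0.4 / −0.3 | 20% | −0.140 | 98.9% | 100% |

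A common additive shift of −0.10 gives bias 0.000 and rejection of 4.4% to 5.5%. The same-pair contrast rejects in 4.4% to 5.6% of replicates in every scenario, at n=25 and at n=50. The two-pair target term, run at z = ±0.3 with 10% attenuation and n=25, rejects in 5.3% (ρ = 0) and 4.8% (ρ = 0.5).

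**Do the planned checks catch it?** Comparing pre-rTMS scans between sessions shows whether the starting level is stable; it contains no post-rTMS scan and cannot see change within a session. The M1/A1/V1 check does look from before to after rTMS, but in other connections, and a non-significant result there does not correct the primary pair. There is no sham, and the optional fourth visit covers at most five subjects.

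**The case against.** The strongest reply is that Section VI never states the stimulated-site contrast. It speaks of change between two given ROIs and compares those z-scores across conditions. Read literally, that is one fixed pair in both sessions, which is already the sound contrast. The stimulated-site reading comes from a hypothesis and a figure caption, and model detail may belong in a statistical analysis plan that is not shown. This stands in part: a reader might infer that the protocol commits to comparing different pairs, and it does not. But a fixed pair would have to name its DLPFC site, and nowhere does the protocol do so. The contrast is listed as a main outcome, so leaving it open to two readings is a defect of the protocol itself.

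Four further points limit the concern:

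- A reader might infer that any change shared by both sessions survives. It does not: the outcome is signed z, and a common additive shift cancels exactly.
- A reader might extend the problem to Hypothesis 1.2 and the secondary pairs. Hypothesis 1.2 refers to cortico-limbic connectivity in general, and sgACC-dmPFC, sgACC-NA and sgACC-amygdala are the same pairs in both sessions.
- A reader might say that attenuation would reproduce Fig 3. It matches the direction of panel B only. Panel C has the anticorrelation strengthening, whereas attenuation weakens it, and the separate pre-to-post tests could show that mismatch.
- Choosing seeds at extreme correlations does not by itself bias the change, because targets come from the visit 1 scan and the change uses separate scans.

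The protocol also screens runs for low signal-to-noise and head movement, which may reduce attenuation but does not remove it from the contrast.

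**Conclusion.** The concern holds as an unresolved definition with a real consequence on one of its two readings. If the stimulated-site pair is used in each session, the contrast estimates the target difference plus cP − cN, and neither counterbalanced order nor the pre-rTMS comparison removes the second part. If each pair is compared with itself, the problem does not arise.

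The false-positive rates are illustrations, not estimates for this trial. They rest on assumed baseline z, attenuation and correlation, and on an SD borrowed from another connection. Their spread, from about 9% to nearly 100%, shows that the result depends on drift the documents do not quantify. The documents do not support a claim that the planned analysis will produce a false target effect. They support the narrower conclusion that the primary across-target test should be fixed before analysis, in the form that is protected from this drift.

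**What to change.** In Section VI (fcMRI data):

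1. State that each sgACC-DLPFC pair, correlated and anticorrelated, is compared with itself between the two randomised sessions.
2. Test whether one target alters connectivity more with the target term of a within-subject model that takes both pairs from both sessions and includes session order. Say that this term compares signed changes in z.
3. Label any contrast of one stimulated site with the other as confounded with ROI pair.
4. As a separate gain in precision, and not a cure for the confounding, adjust the same-pair contrasts for the pre-rTMS z difference instead of using raw change scores. For a difference of 0.075 at n=25, power was 63% with change scores and 83% adjusted (assumed correlations 0.6 within and 0.5 between sessions), or 64% and 72% (0.8 and 0.5).

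The cost is wording only, since both DLPFC ROIs are imaged before and after rTMS in both sessions. The downside is that the same-pair contrast is relative: if stimulating one site also changes the other site's coupling with sgACC, it may be diluted. Its power of over 99% at n=25 therefore holds only for a full 0.15 difference between own-site and other-site stimulation.

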Functional connectivity MRI (fcMRI) relies upon correlations between spontaneous low frequency fluctuations in the blood oxygenation level-dependent (BOLD) signal to delineate intrinsic brain networks in the absence of explicit task demands.²⁷⁻²⁹ fcMRI studies in normals have revealed topographically consistent patterns of functional connectivity among the aforementioned cortico-limbic regions. Using seed based analytic approaches, sgACC has been shown to be functionally correlated to several limbic regions including the OFC, amygdala and NA.^{9,21,22,30} This functional connectivity strongly recapitulates structural projections to and from the sgACC in animal and human studies.³¹⁻³³ In addition, sgACC shares functional connectivity with portions of the default network (DN), specifically the dmPFC⁹, the temporal pole and the posterior cingulate/precuneus (pCC).^{21,22} Relevant to this study, sgACC is functionally correlated to a medial portion of the DLPFC (superior frontal gyrus, a part of the DN), but is anticorrelated to another portion of DLPFC (middle frontal gyrus).^{21,22} These correlation patterns have been borne out within our own data (**Fig 1**).

[figure not shown]

Fig 1. Voxel-wise functional connectivity maps derived from seeding the sgACC in 26 healthy subjects in our lab. In DLPFC, both positive (red/yellow) and negative (blue) correlations are observed.

In MDD, evidence of aberrant network activity was first described in the form of reduced deactivations in the DN during task execution.³⁴⁻³⁵ With regards to functional connectivity, studies suggest that the sgACC and dmPFC⁹ are excessively coupled to their distributed cortico-limbic partners. Resting-state fMRI data have also elaborated abnormal network metrics in MDD, including increased regional homogeneity, increased nodal centrality and connectivity degree, and decreased small-worldness.^{36,37} Notably, these metrics were identified in similar cortico-limbic and default regions, and they correlated with disease severity.

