The subject will also be informed that, at any point, he/she may choose to terminate the study for any reason and that he/she has the option not to participate in the study. This includes being able to terminate the study during the experimental procedures proper. They will be informed that their refusal to participate in the study, or their wish to terminate it at some point, will have no effect on care and treatment received by them at any Partners hospital including the Brigham and Women's hospital and the Massachusetts General Hospital or any of their affiliated institutions, now, or at any time in the future. Should the subject indicate that he/she wishes to participate in the study, written informed consent will be obtained. All participants will be provided with copies of the signed consent form.

V. STUDY PROCEDURES

A. rTMS, PET and fMRI procedures:

fcMRI and PET will be acquired using an integrated Siemens 3.0 T whole-body Siemens MRI scanner fitted with a 3D dedicated BrainPET camera housed at the Athinoula A. Martinos Center for Biomedical Imaging at the MGH Charlestown Navy Yard. This scanner is capable of the simultaneous acquisition of PET and MRI data (**Fig 4**).

fMRI procedures: Structural images will be acquired via a 3D-turbo field echo sequence which will generate high resolution 3D MPRAGE T1-weighted images. Functional images will be acquired using a T2*-weighted sequence. Functional data will be collected by using an asymmetric spin-echo, echo-planar sequence sensitive to BOLD contrast during three 6 minute functional runs while subjects rest and stare at a white fixation

[figure not shown]

Fig 4: Simultaneous MR-PET data acquisition in a healthy subject using the MRI-BrainPET scanner. Axial, coronal and sagittal FDG-PET (upper), fused MR-PET (middle) and MR (lower) are shown.

dot. During this time, subjects will be instructed to lay as still as possible and “think about whatever they want.”

PET procedures:

Subjects will be instructed to fast and not to consume beverages, except for water, for at least 4 hours before the administration of FDG to decrease physiologic glucose levels and to reduce serum insulin levels near basal levels. While fasting, subjects should consume at least two to three 8-12oz glasses of water to ensure adequate hydration.

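### The fcMRI filter is worded to keep frequencies above 0.08 Hz, which contradicts the protocol's own statement that functional connectivity rests on low-frequency BOLD fluctuations

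*Protocol*

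**What the plan says.** Protocol Section VI (Biostatistical Analysis, fcMRI data) gives the only temporal filter in the document: "Preprocessing will include global mean regression and temporal band-passing of data for signals >0.08 Hz". It then says that "After preprocessing, region-to-region correlation strengths will be calculated with volumetric seed-based functional connectivity analyses", so the correlations are computed on the filtered data. The same section defines the outcome: "The main outcome measures of interest for fcMRI data will be the relative change in z-transformed correlation coefficients between two given cortico-limbic network regions".

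Section I (Background and Significance) describes the measure differently. There, functional connectivity MRI "relies upon correlations between spontaneous low frequency fluctuations in the blood oxygenation level-dependent (BOLD) signal to delineate intrinsic brain networks".

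Section V.C uses baseline connectivity maps from an sgACC seed to choose where to stimulate: "these maps will be used to establish two cortical targets for rTMS in DLPFC". It does not say how those maps are preprocessed. Section V.A sets the resting acquisition as "during three 6 minute functional runs while subjects rest and stare at a white fixation" dot. No repetition time is given, and no numeric range is attached to the term low frequency.

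**The concern.** To band-pass data for certain signals is to keep those signals. With 0.08 Hz as the only limit, placed as a lower bound, the written step is a high-pass filter. It removes the low end of the spectrum, where Section I says the signal of interest lies, before any correlation is calculated.

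Several outputs depend on this step: the primary DLPFC-sgACC change, the three secondary sgACC pairs, the M1/A1/V1 inter-hemispheric check and the comparison of pre-rTMS scans between sessions. The last two are read as reassuring when nothing changes. If correlations are pulled toward zero by the filter, a null result there says less than the protocol intends.

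An analyst who follows the text would apply the wrong filter. One who applies the presumably intended filter would depart from the protocol with no record of why.

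**Working it through.** **Side by side.** Section I: the measure is the correlation of low-frequency fluctuations. Section VI: signals above 0.08 Hz are passed, then correlations are computed. No other section gives a second limit or the opposite direction. Both statements cannot describe the same analysis unless low frequency is taken to mean above 0.08 Hz, which nothing in the protocol suggests.

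The protocol has no figure of its own to reproduce here. What follows only illustrates how much correlation could be lost.

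**Set-up (assumptions).** Two regions share one signal. Each also has independent white noise with the same total variance as the signal. The repetition time (TR) is taken as 2 to 3 s. For a filter that keeps a given band, let S be the share of signal power in that band and N the share of noise power. The expected correlation is

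r = S / (S + N).

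With no filter, r = 1/(1 + 1) = 0.50.

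**Case A: shared signal confined to 0.005-0.08 Hz, TR 2.5 s (Nyquist 0.20 Hz).**
- Low band kept: S = 1 and N = 0.075/0.20 = 0.375, so r = 1/1.375 = 0.73 (z = 0.93).
- Filter as written: S = 0, so r = 0.00.
- A simulation of 2,000 pairs with a sharp-edged filter gave 0.73 and 0.00, and 0.50 with no filter. With a 4th-order Butterworth filter, roll-off leaves about 0.00 to 0.03 above 0.08 Hz.

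**Case B: shared signal with power proportional to 1/f^b and no hard cut-off.** The share of power below 0.08 Hz in a 6-minute run is:

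| TR | flat (noise) | b = 0.5 | b = 1 | b = 1.5 |
|---|---|---|---|---|
| 2 s | 0.311 | 0.525 | 0.773 | 0.932 |
| 2.5 s | 0.389 | 0.592 | 0.808 | 0.941 |
| 3 s | 0.467 | 0.654 | 0.839 | 0.950 |

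For b = 1:
- TR 2 s, low band kept: 0.773/(0.773 + 0.311) = 0.71. As written: 0.227/(0.227 + 0.689) = 0.25.
- TR 3 s, low band kept: 0.839/(0.839 + 0.467) = 0.64. As written: 0.161/(0.161 + 0.533) = 0.23.

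For b = 0.5:
- TR 2 s: 0.525/0.836 = 0.63 against 0.475/1.164 = 0.41.
- TR 3 s: 0.654/1.121 = 0.58 against 0.346/0.879 = 0.39.

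For b = 1.5:
- TR 2 s: 0.932/1.243 = 0.75 against 0.068/0.757 = 0.09.
- TR 3 s: 0.950/1.417 = 0.67 against 0.050/0.583 = 0.09.

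Simulations that treat the 18 minutes as one continuous series, with a Butterworth filter, give similar results. For b = 1 they leave 0.20 to 0.21 above the cut-off against 0.66 to 0.73 below it. For b = 0.5 they leave 0.38 to 0.39 against 0.60 to 0.65.

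**Reading.** Whenever the shared signal is concentrated at low frequencies, the filter as written lowers the correlation. The loss is close to total in Case A and partial in Case B. Only a shared signal as flat as the noise (S = N in each band, r = 0.50 in both) would be unaffected, and that is not what Section I describes.

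**The case against.** The strongest reply is that this is a slip of drafting, not a choice of analysis. One open-ended limit does not make a band, so the phrase is already incoherent as a filter specification. The paragraph also refers to methods used in the prior healthy-volunteer study, and a reader of Section I can guess the direction meant. Most of this stands: the likely cause is a reversed sign or an omitted word, and literal execution may be unlikely. It does not remove the point, because the explicit sentence is the only filter stated for the main fMRI outcome and a general reference to earlier methods does not override it. Nor is it a detail left to an analysis plan, since the protocol states the parameter and states it in the wrong direction.

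A second reply is that the illustration builds in its answer by placing the shared signal below 0.08 Hz. That is fair for Case A and is why Case B is shown. The documents establish the direction of the effect but not its size.

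Two stronger readings are tempting and should not be drawn.
- A reader might infer that the 0.15 z change used for sample size in Section III.D could not be detected under this filter. The documents do not support that. The 0.15 (SD 0.11) is an observed parietal-to-medial-prefrontal change in the prior study, not a DLPFC-sgACC change. The calculations above give correlation levels, not the pre/post change, its SD or power under either filter.
- A reader might infer that stimulation sites will be chosen from the wrong band. Section V.C does not state the preprocessing of the Visit 1 maps, so this remains conditional.

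**Conclusion.** The point holds as an internal contradiction between Sections I and VI of the protocol, and the sentence in Section VI should be corrected. As written, it would attenuate the primary and secondary connectivity z values and weaken the two connectivity control comparisons. The illustrated correlation falls from 0.73 to 0.00 if the shared signal lies wholly below 0.08 Hz, and from about 0.64-0.71 to 0.23-0.25 for a 1/f signal. These figures rest on an assumed TR of 2 to 3 s, equal signal and noise variance, white noise and an assumed spectrum, none of which the protocol gives.

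If the Visit 1 maps share this preprocessing, the choice of both DLPFC targets is affected as well, and reanalysis could not undo that once subjects had been stimulated. The PET measures do not pass through this filter; they could be touched only indirectly, through that conditional effect on the sites.

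**What to change.** Reword the Section VI sentence to say that frequencies below 0.08 Hz are retained and signals above 0.08 Hz are removed, in agreement with Section I. Add that the same filter applies to the Visit 1 sgACC maps used for targeting and to every pre- and post-rTMS scan, with a matching cross-reference in Section V.C. A lower cut-off can be given there or left to the analysis plan.

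The cost is a sentence or two of text, with no change to visits, scans or sample size. If any targets have already been chosen, the filter actually used for those maps should be confirmed and recorded.
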